5.3 Informed Consent Procedures

The veteran participants will complete a telephone screen to ensure that they meet basic criteria and to reduce burden for those veterans who would not qualify from the onset. The study will be described to them and if they remain interested in participation verbal permission will be requested to ask the screening questions (See script and flow chart for telephone screen.)

Written and verbal informed consent will be obtained from the veteran participants before implementation of the remaining study procedures. Two consent forms; one for each part of the study and will be completed. The consent form for Part 1 will be completed by all participants and the consent form for Part 2 will only be signed by participants who complete Part 1 and are selected to complete Part 2. Informed consent will be obtained from the participants in person in a private room by the investigators or study staff approved to obtain informed consent. Human subjects protection requirements and how to obtain and document informed consent will be reviewed during the initial training of study personnel to insure procedural uniformity across sites. The training will occur at the beginning of the study and as new personnel are added to the study by the lead investigators at each site.

Written and verbal informed consent will not be obtained from the significant others who complete the HHIA-SO. The instructions will indicate that completion and mailing of the questionnaire will be voluntary and that all information on the questionnaire will be kept confidential and not accessible to the veteran. No identifying information will be requested or included on the questionnaire except for the subject ID number assigned to the veteran participant.

5.4 Inclusion/Exclusion Criteria

The inclusion and exclusion criteria for the veteran participants will be based on the telephone screen and preliminary assessment procedures specified previously. These procedures will be used to form the 4 participant groups and to insure that the participants can complete the tasks (See Table 1 above). All of the participants will be aged 20 to 50 years, have normal or near normal audiometric test results, corrected or uncorrected vision of 20/30 or better, and no evidence of hyperacusis. The mTBI-only group will have a history of blast exposure, evidence of possible brain injury, no significant symptoms consistent with PTSD, but elevated hearing handicap scores on

the Hearing Handicap Inventory for Adults (HHIA). The mTBI+PTSD group will have a history of blast exposure, evidence of possible brain injury, significant symptoms consistent with PTSD, and elevated hearing handicap scores on the HHIA. The PTSD-only group will have no history of blast exposure or brain injury but they will have significant symptoms consistent with PTSD. The Normal control group will have no history of blast exposure or brain injury, and little or no symptoms of PTSD (or other psychiatric disorder) or hearing handicap. All of the veteran participant must not have a history of hearing aid use, or brain injury or disease more severe than that targeted by the study. In addition, the veteran participants must be able to be paid for their participation.

5.5 Study Evaluations

All of the evaluations to be conducted are listed above under study procedures (5.1). The data will be collected by the investigators and study staff. The types of assessment methods vary and include questionnaires, review of records, behavioral tests, and physiological procedures. Some data will be acquired via computer, while others will be administered face to face and via paper-and-pencil.

5.6 Data Analysis

Part 1 Analysis

Preliminary Analyses - The analysis will begin with basic descriptive statistics including means and standard deviations for continuous data and examination of distributional assumptions for all study measurements including the questionnaire data (e.g., HHIA, WHODAS-II, SSQ and HHIA-SO) for each group of interest. These analyses will be used to evaluate the extent of missing data and to identify outliers.

Primary Analyses - Random Forests (RF, Breiman, 2001) will be applied to determine which auditory, language processing, and executive function variables best discriminate the three groups. This technique performs variable selection and the variables are ranked by Gini score, a measurement of average accuracy of all trees containing a particular variable. One-way ANOVA will be used to determine differences between groups for normally distributed continuous data. Analysis of covariance (ANCOVA) will be used to adjust for differences between groups. If assumptions for the parametric test are not met, a non-parametric alternative will be used (e.g., Kruskal-Wallis, non-parametric ANCOVA). The p-values will be adjusted for multiple testing by using a false discovery rate method whenever more than one variable is being tested. Statistical assumptions (e.g., linearity, normality) will be verified prior to hypothesis testing. All statistical analyses will be two sided and the significance level will be 0.05.

Sample Size and Power - A sample size of 117 per veteran group will achieve 80% power at a 0.05 significant level to detect an effect size (i.e., odds ratio) of 2.50. This sample size was computed based on an adjustment that was made assuming that a multiple regression of the independent variable of interest on the other independent

variables in the model will result in an R-squared of 0.20. For one-way ANOVA, the total sample of 468 subjects achieves 80% power to detect an effect size of 0.18 or larger with a two-sided significance of 0.01 to account for multiple hypotheses testing. For analysis of covariance, the study is powered (0.80) to detect an effect size of 0.16 assuming the strength of the relationship between the response of interest and the covariates, measured as R-squared, is 0.20.

Part 2 Analysis

Primary Analyses – Basic descriptive statistics will be computed and examination of statistical assumptions will be performed for all study measurements. For questionnaire data, analysis of variance (ANOVA) or Kruskal Wallis test will be used to determine differences in the overall and subset scores between the mTBI groups. The analysis will also include basic descriptive statistics for behavioral data test measures at baseline and at 6 months for the mTBI-only and mTBI+PTSD groups, and at baseline and 12 months for the delayed-treatment groups. We will focus on the changes in the behavioral test measures from baseline to 6 months (mTBI-only and mTBI+PTSD treatment groups) and from baseline to 12 months (delayed-treatment groups). Specifically, paired t-test or Wilcoxon signed rank test will be used to determine change at 6 or 12 months and this test will be applied to each behavioral test measure separately. False discovery rate will be used to adjust the p-values for multiple hypotheses testing. All statistical analyses will be two sided and the significance level will be 0.05.

Secondary Analyses – For longitudinal analysis, the data will be modeled using linear-mixed models for which the outcome is the behavioral test measure across time. The predictors will include time, group and interaction between group and time. Covariates will be added to the model as needed. In addition, variables with a high Gini score from Part 1 will be correlated with final hearing aid results as a preliminary investigation of whether hearing aid benefit can be associated by any of the variables obtained above. We will measure correlations using either Pearson's or Spearman's correlation coefficient. We will adjust the p-values for multiple testing by using a false discovery rate method whenever more than one variable is being tested. Single-subject design metric also will be used to investigate individual responses to the hearing aid treatment.

Sample Size and Power – This analysis will include data from 100 participants (25 for each group). For any comparisons of the four groups based on ANOVA with a significance level of 0.01 to account for multiple comparisons and a power of 0.80, an effect size of 0.38 or greater will be detectable. For the paired analyses described above, there is sufficient power (0.80) to detect an effect size of 0.50 (baseline versus 6 months) or 0.50 (baseline versus 12 months), or greater assuming a two-sided significance level of 0.01 to account for multiple comparisons. For the longitudinal modeling, there will be sufficient sample size to support the proposed modeling that will allow approximately 10 observations to be estimated for each parameter. The number of covariates in each model will depend on the sample size to insure that there are approximately 10 observations available for each parameter estimated. For correlation

based analyses, the study is powered (0.80) to detect correlations of 0.26 or greater in absolute value for a total sample size of 100.

Once the data are formatted and cleaned by a staff member at the VA Pittsburgh site under the supervision of the statistician, the data will be analyzed by the statistician.

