3.0 Objectives

The purpose of the current proposal is to examine the characteristics and nature of this population's auditory and auditory-related skills, and assess whether coexisting PTSD contributes to their deficits. A group of these veterans will be grouped by whether they are symptomatic for PTSD, and will be compared to a control group of veterans without auditory complaints, and no PTSD or history of blast exposure. Comparisons also will be made to a group of veterans with no significant blast histories and with disabilities limited to PTSD.

After completing a clinical audiometric test battery, and PTSD, TBI, hearing handicap, and vision screens the veterans will complete measures of quality-of-life, central auditory processing, speech perception in noise, language processing and executive function to better understand various aspects of their ability to hear, remember, attend to and process speech and language through audition. The procedures will provide information about the loci of their auditory deficits and determine the extent to which language processing load and PTSD play a role. Secondarily, we will assess whether this population of veterans benefits from mild-gain open-fit hearing aids and if PTSD influences outcomes.

The information obtained from this study will help us understand the auditory problems experienced by these veterans, and eventually contribute to the development of an efficient and effective assessment battery and intervention approaches. This study is framed from both a behavioral and physiological perspective in order to document the problems experienced by this group of veterans. The tasks in the current proposal will provide insight into this population of veterans and lay the groundwork for future research looking at auditory-specific disorders secondary to blast-exposure and mTBI. The current study also will provide background support for a more extensive intervention study with this population.

Specific Questions to be Addressed

- a. Across a range of central auditory processing, speech perception, psychoacoustic, verbal working memory, and language processing tasks, does this population of veterans differ from veterans who have normal hearing and no auditory complaints? Moreover, does the coexistence of PTSD influence performance?

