- b. Are certain test procedures and stimuli particularly sensitive to the deficits found with this population of veterans and are deficit patterns influenced by the coexistence of PTSD?
- c. Does the addition of background noise produce over-additive effects in this population of veterans and does PTSD increase the effect?
- d. Does this population of veterans perceive and demonstrate benefit when fitted with hearing aids that provide mild high-frequency gain and does PTSD influence benefit?
- e. Is hearing aid benefit predictable by measures of auditory processing, speech perception, psychoacoustic, verbal working memory, and language processing? Furthermore, does the coexistence of PTSD influence the relationship between these measures and hearing aid benefit?

Expected Outcomes

- a. This population of veterans will differ from veterans with no history of blast exposure, and the presence of PTSD will increase severity and alter the deficit pattern.
- b. This population of veterans will experience significant problems with the addition of background noise and the effect will be influenced by linguistic load, verbal working memory and attention.
- c. This population of veterans will demonstrate and perceive benefit from being fitted with mild-gain high-frequency hearing aids, although the coexistence of PTSD will restrict perceived benefit.
- d. Mild-gain high-frequency amplification will improve speech perception skills in quiet and noise, and improve linguistic processing and executive function.
- e. Benefit from amplification will relate to the deficits that the veterans present.

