- d. Staggered Spondaic Word Test (SSW) to measure timing and inter-hemispheric processing of words
- e. Gaps in Noise Test (GIN) to assess temporal processing in noise
- f. Auditory brainstem response (ABR), middle latency response (MLR), long-latency response (LLR) and active event-related P300 to assess the electrophysiological status of the central auditory system.

Speech and Language Processing in Noise –

- a. The Words-in-Noise test (WIN; VA Compact Disk 4.0; Wilson & Burk, 2005) to target listening at the single word level
- b. The Listening in Spatialized Noise - Sentences Test (LiSN-S; Cameron & Dillion, 2012) to assess sentence perception in noise within a simulated 3-dimensional acoustic space
- c. Auditory and reading versions of subtests 1 through 10 from the Computerized Revised Token Test (CRTT and CRTT-R respectively; McNeil et al., 2009) will be administered in quiet and in +3 dB signal-to-babble to assess sentence level processing in both auditory and reading domains. The preliminary CRTT pretests will be administered prior to these tests to assure that the participants have the basic skills to complete the tasks and to measure baseline reaction time.

Executive Function –

- a. Digit span forwards and backwards both acoustically and visually according to Kemtes and Allen (2008) to assess verbal short term and computational memory skills
- b. The CRTT Stroop task (CRTT-R-Stroop; McNeil et al., 2010) to assess the interaction between language and executive function
- c. Rey Auditory Verbal Learning Test (Schmidt, 1996) to assess immediate and delayed verbal memory, efficiency of learning and the effects of interference
- d. Trail Making Test (Reitan, 1992) to measure attention and processing speed

PART 2 Procedures

Hearing Aid Fittings (treatment groups) – In Part 2 a subset of the participants from the mTBI-only and mTBI+PTSD groups from Part 1 will be fitted binaurally with open-fit hearing aids with mild high-frequency gain. Each group will consist of 25 participants. They will be randomly selected and randomly replaced if they decline to participate at any point during the treatment protocol.

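### Question c (over-additive noise effect, and whether PTSD increases it) has no specified Part 1 test: section 5.6 names no quiet-versus-babble term, difference score or group-by-condition contrast

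*Combined protocol and SAP*

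**What the plan says.** Question c in section 3.0 reads: "Does the addition of background noise produce over-additive effects in this population of veterans and does PTSD increase the effect". Section 5.1, under speech and language processing in noise, supplies the paired data. The auditory and reading versions of the CRTT "will be administered in quiet and in +3 dB signal-to-babble to assess sentence level processing in both auditory and reading domains".

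The Part 1 primary analyses in section 5.6 are:

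- Random Forests, to rank variables;
- group comparisons: "One-way ANOVA will be used to determine differences between groups for normally distributed continuous data";
- ANCOVA to adjust for group differences;
- non-parametric alternatives where assumptions fail;
- a multiplicity rule: "The p-values will be adjusted for multiple testing by using a false discovery rate method whenever more than one variable is being tested".

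The only interaction anywhere in section 5.6 is group by time, in the Part 2 secondary analyses. The Part 1 power statement for ANOVA is that "the total sample of 468 subjects achieves 80% power to detect an effect size of 0.18 or larger with a two-sided significance of 0.01".

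**The concern.** Over-additivity is a statement about an interaction: the deficit relative to controls is larger in babble than in quiet. The PTSD half of the question is also an interaction: the extra loss in babble is larger in mTBI+PTSD than in mTBI-only. A one-way ANOVA has group as its only factor. Run on the quiet score and again on the babble score, it says whether groups differ in each condition, not whether the difference changes between them.

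Two misreadings become possible. A general deficit, equal in both conditions, gives significant results in both and may be reported as a noise problem. A result that is significant in babble but not in quiet may be reported as over-additive, although the two differences were never compared. Because the derived score, its scale and the contrasts are not fixed, the analyst would also choose them after seeing the data.

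**Working it through.** **Inputs from the documents.** Four groups of 117 (N = 468); alpha 0.01 for power planning and 0.05 for analysis, both two-sided; power 0.80; ANOVA effect size 0.18, read as Cohen's f.

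**Inputs assumed.** An illustrative 0.5 SD deficit. Also the quiet-babble correlation rho and the ratio of the quiet to the babble SD, neither of which the documents give.

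**1. The plan's own figure.** Noncentral F with 3 and 464 df and lambda = N f² = 468 × 0.18² = 15.16. Power at alpha 0.01 is 0.783, and 80% power needs f = 0.183. The stated figure therefore reproduces to rounding as a four-group omnibus test on one variable. It does not describe a test of question c.

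**2. What separate ANOVAs show when there is no interaction.** Let both mTBI groups be 0.5 SD below the other two groups, equally in quiet and in babble. The group means are 0, 0, −0.5, −0.5. Their standard deviation is 0.25, so f = 0.25.

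- Each condition: lambda = 468 × 0.25² = 29.25; power at alpha 0.01 = 0.988.
- Babble minus quiet: every group has the same mean change, so the interaction is exactly zero.

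Both ANOVAs would almost always reject while the answer to question c is no.

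**3. What the missing contrasts can detect.** Work on babble-minus-quiet in units of its own SD, with the pooled error of the four-group model (464 df). The smallest detectable difference is approximately (z for alpha + z for power) × sqrt(1/n1 + 1/n2). The exact noncentral-t value agrees to two decimals unless shown.

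- (i) Both mTBI groups v Normal Controls, 234 v 117: sqrt(1/234 + 1/117) = 0.1132. At alpha 0.01, (2.576 + 0.842) × 0.1132 = 0.387 (exact 0.388), so 0.39. At alpha 0.05, (1.960 + 0.842) × 0.1132 = 0.317, so 0.32.
- (ii) mTBI+PTSD v mTBI-only, 117 v 117: sqrt(2/117) = 0.1307. At alpha 0.01, 3.418 × 0.1307 = 0.447 (exact 0.448), so 0.45. At alpha 0.05, 2.802 × 0.1307 = 0.366 (exact 0.367), so 0.37.

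**4. Conversion to single-condition SD.** With equal SDs in quiet and babble, the difference score has SD = sqrt(2(1 − rho)). With the quiet SD half the babble SD, it is sqrt(1.25 − rho) babble SDs. For contrast (ii) at alpha 0.01, multiplying by 0.448:

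| Assumed rho | Equal SDs | Quiet SD half of babble SD |
|---|---|---|
| 0.3 | 0.53 | 0.44 |
| 0.5 | 0.45 | 0.39 |
| 0.7 | 0.35 | 0.33 |
| 0.8 | 0.28 | 0.30 |

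**5. Why the 3-df interaction test cannot carry the question alone.** Suppose only the PTSD-only group loses an extra 0.45 difference-score SD in babble. Then f = 0.45 × sqrt(3)/4 = 0.195, and the 3-df test has power 0.862 at alpha 0.01. Yet PTSD-only enters neither contrast (i) nor contrast (ii).

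**The case against.** The best reply is that section 5.6 does not list the dependent variables. A one-way ANOVA of babble-minus-quiet is algebraically the group-by-condition test, and an ANCOVA of babble with quiet as covariate is a related option. Both fit the listed methods, and the group means promised in the descriptive analysis would let a reader form a difference of differences. This stands. A reader might infer from the gap that the plan is unable to test question c, or that it cannot separate a general deficit from a noise-specific one. The documents do not support that; they support only that no such analysis is specified. The reply does not close the gap, because the difference score and the ANCOVA can give different answers and nothing says which will be used.

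A second reply is that Part 1 is a first, characterising study. But question c is one of five listed questions, section 3.0 states an expected outcome on noise in advance, and section 5.6 calls these analyses primary.

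A reader might also take mTBI-only v Normal Controls as the natural test of over-additivity. Sections 3.0 and 5.1 define the target population as the veterans with blast exposure and auditory complaints and then split them by PTSD, so that contrast alone drops half of the population asked about.

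Finally, a reader might extend the gap to question a ("Moreover, does the coexistence of PTSD influence performance"). There the PTSD comparison, mTBI+PTSD v mTBI-only, is estimable from the group factor. It is merely not named, and the stated ANOVA power covers only the omnibus test. That is a remark, not part of this finding. Nor does the finding rest on the odds-ratio power statement ("A sample size of 117 per veteran group will achieve 80% power at a 0.05 significant level to detect an effect size") or on the reference to variables that "auditory, language processing, and executive function variables best discriminate the three groups" in a four-group design; these are separate matters.

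**Conclusion.** The point holds as a pre-specification gap: a listed study question has its data scheduled but no analysis assigned to it. The per-condition ANOVAs cannot substitute, since under an equal 0.5 SD deficit each rejects with power 0.988 while the interaction is zero. That 0.5 SD is illustrative; the logic holds for any equal shift.

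The detectable effects of 0.39 and 0.45 difference-score SD at alpha 0.01 (0.32 and 0.37 at 0.05) rest on 117 completers per group, a common error variance and no further multiplicity adjustment. Any restatement in single-condition SD rests in addition on an assumed correlation and an assumed SD ratio. The PTSD groups are formed by PCL-M score, not by randomisation, so contrast (ii) describes an association with PTSD symptoms and does not isolate a PTSD effect.

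**What to change.** In the Part 1 primary analyses of section 5.6:

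1. State that the outcome for question c is babble-minus-quiet on the auditory CRTT, or the equivalent group-by-condition repeated-measures model. Fix the score scale in advance, including any transformation for ceiling scores in quiet.
2. Name two 1-df contrasts within the four-group model: (i) both mTBI groups v Normal Controls for over-additivity, with mTBI-only v Normal Controls as a supportive version free of PTSD; (ii) mTBI+PTSD v mTBI-only for whether PTSD increases the effect. Make the 3-df test supportive.
3. Analyse CRTT-R in the same way as a comparison. The abstract gives the reading test the purpose of showing whether problems are limited to the auditory system.
4. Word the false discovery rule to cover these contrasts, since it now refers only to variables.
5. Beside the omnibus figure, state the detectable effects above in difference-score SD. Label any conversion to single-condition SD as assuming both the correlation and equal quiet and babble SDs.

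The cost is analysis wording only; both conditions are already scheduled. The downsides are a slightly larger false discovery family and an interaction whose size, and possibly presence, depends on the score scale. The change does not test the moderators in the expected outcomes (linguistic load, verbal working memory, attention).

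### Part 1 asks whether PTSD changes the pattern of deficits as well as their severity, but no planned analysis tests pattern, and reading it from lists of significant tests can mistake a uniform shift for a changed pattern

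*Combined protocol and SAP*

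**What the plan says.** Section 3.0 Objectives, Specific Question b, asks which tests are sensitive to this population's deficits and then: "are deficit patterns influenced by the coexistence of PTSD". Expected Outcome a makes two claims: "the presence of PTSD will increase severity and alter the deficit pattern".

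Section 5.6, Part 1 Primary Analyses, has two tools. The first is Random Forests, used to "determine which auditory, language processing, and executive function variables best discriminate the three groups", with variables ranked by Gini score. The text does not say which three of the four groups are meant. The second is a group comparison: "One-way ANOVA will be used to determine differences between groups for normally distributed continuous data", with ANCOVA for adjustment and non-parametric substitutes. The plan does not say in so many words that each test gets its own ANOVA, but the adjustment rule implies it: a "false discovery rate method whenever more than one variable is being tested".

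Part 1 has no common scale across tests, no group-by-test term, no profile analysis and no named contrast of mTBI+PTSD with mTBI-only. The only interaction in section 5.6 is group by time, in the Part 2 secondary analyses.

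**The concern.** Severity and pattern are different hypotheses. If PTSD lowers every test by the same standardised amount, severity rises and the pattern is unchanged. Pattern changes only if the PTSD difference varies across tests, so testing it means comparing differences between tests within one analysis. The Part 1 plan never does this.

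The second half of question b and half of expected outcome a therefore have no planned answer. The obvious substitute is to list the tests that are significant in one mTBI group and not in the other, or the tests on which the two groups differ significantly. When power per test is moderate, such lists split by chance even if the true shift is identical everywhere. The results are meant to inform an assessment battery, so a false pattern could affect which tests are chosen.

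**Working it through.** **1. The plan's own figure.** Section 5.6 states that "the total sample of 468 subjects achieves 80% power to detect an effect size of 0.18 or larger" at a "two-sided significance of 0.01 to account for multiple hypotheses testing". With four groups and f = 0.18, lambda = N·f² = 468 × 0.0324 = 15.16 on 3 and 464 df. Power from the noncentral F at alpha 0.01 is 0.783, and the f detectable with 80% power is 0.183, which rounds to 0.18. The figure reproduces. It concerns the omnibus four-group test on one variable. No power is stated for pattern.

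**2. A relevant size of PTSD shift.** If f = 0.18 were entirely a PTSD main effect with half the participants symptomatic, d = 2f = 0.36 SD.

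**3. Why lists split.** With 117 per group the standard error of a difference is √(2/117) = 0.131 SD. A true shift of 0.3 SD gives an expected z of 0.3/0.131 = 2.29. Unadjusted two-sided power per test at 0.05 is 0.33 at 0.2 SD, 0.63 at 0.3, 0.86 at 0.4, 0.97 at 0.5 and 1.00 at 0.8. In the middle of that range each test is closer to a coin toss than to a certainty.

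**4. Simulation with no change of pattern.** From the plan: 117 per group and false discovery rate control at 0.05. Assumed: 20 tests, between-test correlation r of 0.3 or 0.5, equal SDs, no missing data, mTBI effect 0.5 SD, and the same PTSD shift on every test (800 trials per setting). A mixed result means that some but not all mTBI+PTSD v mTBI-only contrasts are significant.

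| PTSD shift (SD) | Mean share of tests flagged, r=0.3 / 0.5 | Mixed result, r=0.3 / 0.5 |
|---|---|---|
| 0 | 0% / 1% | 4% / 5% |
| 0.2 | 18% / 18% | 58% / 44% |
| 0.3 | 52% / 51% | 89% / 73% |
| 0.36 | 72% / 70% | 85% / 68% |
| 0.4 | 82% / 81% | 78% / 60% |
| 0.5 | 97% / 96% | 35% / 24% |
| 0.8 | 100% / 100% | 0% / 0% |

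At 0.36 SD with 10 to 30 tests, the range was 55-90%. With 26 scores (one per listed test or condition, an assumption) and r of 0.2 or 0.4, a 0.3 SD shift gave mixed results in 82-96% of trials.

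**5. Lists against controls.** With 26 scores, an mTBI deficit of 0.3 SD and a further uniform 0.2 to 0.4 SD for PTSD, the two mTBI groups' lists disagreed on 44-50% of tests on average. This depends on the mTBI deficit: with 20 tests and a 0.5 SD deficit, the lists differed at all in only 21-49% of trials.

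**6. The omnibus ANOVA alone.** With the mTBI deficit at 0.5 SD and a PTSD shift of 0.2 SD or more, it gave a mixed result in 1% of trials or fewer. With both at 0.3 SD (r = 0.3) it did so in 26%.

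**7. A profile test on such data.** Take q = K − 1 differences between tests and compute T² = (n/2)·d′S⁻¹d, then F = T²(2n − q − 1)/[(2n − 2)q] on q and 2n − q − 1 df. For 26 scores, q = 25 and the denominator df are 234 − 25 − 1 = 208. Under a uniform shift it rejected in about 3.5-7% of trials (nominal 5%). With a true pattern, 8 of 26 tests worse by 0.5 SD, it rejected in essentially every trial.

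**8. The form of the model matters.** A simpler model with group, four test domains, group-by-domain and one participant intercept is not safe. Under a uniform shift it held 5% when all correlations were equal, but falsely declared a pattern in 35-48% of trials when tests correlated more within domains than between (for example 0.4 v 0.2). A multivariate test on the four domain means rejected in 4.6%. With a true pattern spread across all four domains and equal correlations of 0.3, the group-by-domain test rejected in about 5% of trials and the test-level profile test in 100%.

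**The case against.** The strongest reply is that the quoted ANOVA is not what fails. It is an omnibus test that does not contrast the two mTBI groups, and step 6 shows that it seldom produces a split list when the mTBI deficit is 0.5 SD. The high rates in steps 4 and 5 come from pairwise readings that the plan does not name, and nowhere does it say that pattern will be judged by comparing lists. This stands: the rates describe a likely substitute for a missing analysis. It also confirms the gap, because the written test does not address PTSD's effect on pattern at all.

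Second, Random Forests enters the measures jointly, so it would be wrong to say that no analysis uses more than one test. The sample-size text also refers to an odds-ratio model adjusted for other independent variables. Both are true, but a Gini ranking orders variables by how well they separate groups, and neither method tests whether the PTSD difference is equal across tests.

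Third, the problem fades as the shift grows, and the protocol calls the study a first step. Both are fair limits on its weight.

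A reader might infer that a uniform PTSD effect will be reported as a changed pattern, with error in that direction only. The documents do not support this: it depends on the size of the shift and on how authors read the results, and a one-directional error has not been shown.

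**Conclusion.** The gap is clear from the text: followed exactly, Part 1 cannot separate a uniform PTSD deficit from an altered pattern. The consequence is conditional. If pattern is read from pairwise significance lists, a uniform shift gives a mixed list in roughly 45-95% of trials at 0.2 to 0.4 SD, a range that includes the 0.36 SD corresponding to the plan's own f. The rate falls to 24-35% at 0.5 SD and to none at 0.8 SD. These figures rest on assumed numbers of tests, correlations and equal SDs, with complete data. Random Forests was not simulated, so nothing numerical is claimed about its rankings. The point merits a change to the plan because pattern is a stated question, but it does not undermine the per-test group comparisons themselves.

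**What to change.** Add to section 5.6, Part 1:

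- Fix the list of scores that enter the profile. Standardise each to the Normal Control mean and SD, signed so that higher is worse.
- For mTBI+PTSD v mTBI-only, prespecify a group-by-test profile (parallelism) test with unstructured covariance: Hotelling/MANOVA on differences between tests, or the equivalent mixed model, with the ANCOVA covariates. The interaction answers pattern and the group main effect answers severity.
- If a domain summary is also wanted, use a multivariate test on the four domain means or an unstructured domain covariance, not a single participant intercept. It supplements the test-level analysis, since question b is about particular tests.
- State that a claim of a different pattern requires the interaction test, and that per-test results are descriptive follow-up.

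The cost is SAP wording and a little more analysis on data already collected. There are two downsides. Ceiling effects can bend z-score profiles, so repeat the analysis on rank-normalised scores. The multivariate test needs complete data, or else a likelihood-based mixed model. With 26 scores, that model's unstructured covariance has 26 × 27/2 = 351 parameters for 2 × 117 = 234 participants, so a shorter list of scores would help.
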